8.1.6 Outcome of Adverse Events

Study Number: YHCT-HEX-B1

All adverse events must be followed for a final outcome until the end of the period of observation. Related and/or serious adverse events must be followed until resolved, or at the latest until the database is locked. In case of permanent impairment, the event must be followed until the condition stabilizes and the investigator considers is medically justifiable to terminate follow-up, or until database lock.

For adverse events resulting in death, a full pathologist report should be supplied if possible.

Outcome will be recorded in the eCRF as one of the following:

- Resolved
- Resolving
- Not resolved
- Resolved with sequelae
- Unknown
- Death

8.2 Serious Adverse Events

8.2.1 Definition of Serious Adverse Event

A serious adverse event is any untoward medical occurrence that at any dose:

- 1) Results in death
- 2) Is life threatening, the term "life threatening" in the definition of "serious" refers to an event in which the patient was at risk of death at the time of the event; it does not refer to an event which hypothetically might have caused death if it were more severe.
- 3) Requires inpatient hospitalization or prolongation of existing hospitalizationⁱⁱⁱ
- 4) Results in persistent or significant disability/incapacity^{iv}
- 5) Is a congenital anomaly/birth defect
- 6) Other medically important condition

In addition, medical and scientific judgment is required to decide if prompt notification is required in other situations, i.e., any event which the investigator regards as serious that did not strictly meet the criteria above but may have jeopardized the patient or required intervention to prevent one of the outcomes listed above, or which would suggest any significant hazard, contraindication, side effect or precaution that may be associated with the use of the drug.

8.2.2 Reporting of Serious Adverse Events

All SAEs occurring in the period of observation, whether or not related to the study intervention, must be collected and reported to the sponsor / CRO safety contacts and regulatory authority.

SAE occurring after the period of observation should be reported by the investigator to the sponsor /CRO if the investigator considers the SAE to be causally related to the study intervention.

Study Number: YHCT-HEX-B1

An SAE report consists of the following:

- SAE form (available in Investigator Site File and electronically)
- Adverse event form
- Concomitant medication form
- Medical history form
- Bladder cancer medical history

The initial report must be as complete as possible, including all items on the SAE form, otherwise the complete SAE form will need to be sent to the sponsor /CRO Security contacts. The SAE form should preferably be completed electronically. The investigator should report SAE to the sponsor /CRO Security contacts via SAE Manager System (preferred) or email to [contact] and [contact] (when system error) within 24 hours following knowledge of the event.

The investigator should not await additional information to fully document the event before reporting an SAE, although additional information may be requested. Where applicable, information from relevant laboratory results, hospital case records and autopsy reports should be obtained. The investigator is also required to submit follow-up reports until the SAE resolves, or in the case of permanent impairment, until the SAE stabilises.

Information not available at the time of the initial report (e.g., end date for the adverse event or laboratory values received after the report) must be documented as a follow-up report. A new SAE form must be completed, and marked as "Follow-up".

Details of all SAEs must also be reported on the adverse event form in the eCRF.

If an adverse event initially recorded as non-serious event, becomes serious, this must also be reported within 24 hours following knowledge.

The sponsor will report all SAEs to local health authorities and investigators as required by local regulations and sponsor standard operating procedures (SOPs). The investigator is responsible for reporting SAEs to the Institutional Review Board (IRB) according to local requirements.

8.3 Suspicious and Unexpected Serious Adverse Reactions

8.3.1 Definition of Suspicious and Unexpected Serious Adverse Reactions

Suspicious and unexpected serious adverse reactions (SUSAR) refer to those with the nature and severity of the clinical manifestation beyond the information of the existing materials such as the Investigator's Brochure of the investigational drug.

8.3.2 Reporting of Suspicious and Unexpected Serious Adverse Reactions

There is no time limit for the collection of serious adverse events judged to be related to the investigational drug. This means that serious adverse events related to the investigational drug that even occur after the last visit specified in the protocol should still be reported. The reporting method for SUSAR that occurs after the clinical trial is completed and before the approval conclusion is obtained is consistent with that before the trial is completed.

Study Number: YHCT-HEX-B1

The sponsor and/or sponsor representative will report SUSARs to health authorities, ethics committees and investigators, etc. as required by local regulations, sponsor standard operating procedures (SOPs) and other internal references (e.g. Safety Management Plan).

8.4 Reporting of Pregnancies

If a patient or patient partner becomes pregnant during study participation, the investigator must report the pregnancy to the sponsor / CRO safety contacts within 24 hours following knowledge of the pregnancy, reporting method is the same as the SAEs above. The pregnancy should also be recorded in the eCRF.

Patients who become pregnant during study participation will be followed until completion of pregnancy. The pregnancy outcome information must be submitted to the sponsor as soon as it becomes available by completing the pregnancy surveillance form part II. The investigator is responsible for reporting any pregnancies to the IRB.

8.5 Sensitization Risks and Management Measures

Hexvix[®] has the potential to cause rapid-onset severe allergic reactions / hypersensitivity reactions, for which the Sponsor has developed a risk management plan and is managing this as a "significant identified risk".

The routine risk preventive measures that the Sponsor takes concerning this risk are as follows:

- 1. In this clinical trial, subjects with allergy to hexaminolevulinate hydrochloride or a similar compound will be excluded;
- 2. The information on the safety profile of Hexvix concerning allergy occurring in preclinical studies, clinical studies and postmarketing exposure is fully described and prompted in the investigator brochure.
- 3. Information on risks is provided in the clinical use instructions: 【Contraindications】 Hypersensitivity to the active substance or to any of the excipients. Porphyria. 【Special warnings and precautions for use】 The possibility of hypersensitivity including serious anaphylactic/anaphylactoid reactions should always be considered. Advanced life support facilities should be readily available. 【Undesirable effects】 Adverse reactions from clinical trials and spontaneous reporting: immune system disorders anaphylactoid shock.

Study Number: YHCT-HEX-B1

9. Data Management

9.1 Data Management Process

Sponsor or delegate CRO is responsible for the study data management to ensure the authenticity, integrity, privacy and traceability of clinical trial data.

9.2 Database Design and Establishment

The eCRF database is constructed by Sponsor or delegate CRO. The database should manage data traces such as system login, data entry, modification, or deletion, and the establishment of the database shall adopt the CDISC standard.

9.3 Data Entry

Information will be entered into the Electronic Data Capture (EDC) database by the investigator or a person authorized by the investigator within 3-5 working days after completion of the visit. And strictly follow the "what you see is what you record" principle of data entry. After the original data is entered, any changes made to the eCRF are automatically recorded in the system.

9.4 DataVerification

According to the finalized Data Verification Plan (DVP), Data Manager (DM) will set up Data logic verification procedures in the EDC system.

After data entry into the EDC system, if there is any illogical data, the system check will start operation and trigger the challenge. These queries need to be reviewed and answered by the investigator or a person authorized by the investigator. When the updated data makes the logical check no longer valid, the data challenge is closed immediately; If the site confirms the data and provides a response, the DM will review the response information. When the reason is reasonable, turn off the data query; When the data problem is not solved, DM can continue to communicate with the site by adding data query until the final solution.

Generate subject data lists/reports programmatically to support manual data verification throughout the study. When there is data that needs to be clarified/verified/confirmed by the researcher, human questioning can be added to the EDC system. The data manager should confirm that all queries have been resolved and the investigator should complete the electronic signature in the EDC system to ensure the integrity and accuracy of the subject data in the EDC system.

9.5 Medical Coding

The data manager (DM) is responsible for the medical coding of this study. The code includes medical history, concomitant medications, and adverse events.

Previous medical history and adverse events will be coded according to the Medical Dictionary for Regulatory Activities (MedDRA) dictionary. The concomitant drug use was coded by the World Health Organization Drug Dictionary (WHO DD), which adopted the version confirmed by the sponsor.

In the process of coding, DM will ask investigators to verify and confirm any data problems that cannot be encoded due to improper, inaccurate or vague medical terms.

Study Number: YHCT-HEX-B1

Before the database is locked, DM will send a medical coding report to the sponsor and it will be reviewed by the sponsor.

Study Number: YHCT-HEX-B1

10. Statistical Considerations

10.1 General Principle

The Statistical Analysis Plan is prepared by the Biostatistician and the Principal Investigator according to the study protocol and will be finalized and documented prior to the first database lock. Detailed statistical analysis methods will also be specified in the statistical analysis plan.

All statistical analyses will be completed using SAS version 9.4 or higher. See statistical analysis plan for specific statistical methods.

Continuous variables will be described by mean, standard deviation, median, first quartile, third quartile, maximum and minimum.

Categorical variables will be described by frequency and percentage. If necessary, 95% confidence interval (95% CI) of the percentage will be calculated.

10.2 Determination of Sample Size

Approximately 380 subjects will participate in the study and will continue until 94 subjects with pathologically confirmed of bladder cancer at Ta, T1, and CIS stages.

The sample size calculation for this study is as follows:

The primary efficacy endpoint of this study is "The proportion of patients with histology-confirmed tumors (Ta, T1, or CIS) who have at least one such tumor found by Hexvix but not by white light cystoscopy. A proportion of 10% is considered clinically significant, and if the actual proportion is 20%, that is, the null hypothesis is P null hypothesis = 10% and the alternative hypothesis is P alternative hypothesis = 20%, a total of 94 subjects with pathologically confirmed Ta, T1, and CIS stage bladder cancer are required at a one-sided significance level of 0.025 with 80% power based on an exact test for one proportion.

Assuming that 35% of subjects will have bladder cancer after Hexvix-assisted blue light cystoscopy and/or white light cystoscopy, bladder cancer with Ta, T1 and CIS stage accounting for 75%, 359 subjects are expected to be enrolled in this trial. Considering the 5% drop-out rate, a total of about 380 subjects are required. The study will continue until 94 subjects have bladder cancer after Hexvix-assisted blue light cystoscopy and/or white light cystoscopy and are pathologically confirmed as Ta, T1, and CIS stage bladder cancer.

Note: A minimum of 4 subjects included at each center will be training subjects, and those training subjects are in addition to the estimated sample size. Moreover, training subjects are not included in the randomization procedure and efficacy endpoints analysis set, but included in the safety analysis set.

10.3 Statistical Analysis Populations

10.3.1 Safety Set

All subjects who receive Hexvix instillation will be included in the safety population (including training subjects for investigators).

10.3.2 Full Analysis Set

Version 2.2 Date: Feb 6th, 2023 47 | 60

Study Number: YHCT-HEX-B1

10.3.2.1 Full Analysis Set (FAS)

All secondary efficacy analysis will be based on full analysis set (FAS). Subjects who receive Hexvix instillation and undergo blue light cystoscopy will be included in FAS. Efficacy data of subjects who received Hexvix and white light cystoscopy but did not continue with blue light cystoscopy will be shown in individual table. Training patients who receive Hexvix and white light cystoscopy and blue light cystoscopy and have evaluable data will not be included in FAS.

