Patients	1. Gross haematuria. (Note: Gross haematuria is defined as a heavy bladder bleed resulting in marked amounts of blood in the urine, which may visually limit cystoscopy. Where the haematuria is light, the patient should not be excluded, if in the investigator's opinion, rinsing and/or electro-cautery during cystoscopy will alleviate the possible interference with cystoscopy).
	2. Patients who received BCG immunotherapy or intravesical chemotherapy within 6 weeks prior to the procedure.
	3. Porphyria.
	4. Known allergy to hexaminolevulinate hydrochloride or a similar compound.
	5. Pregnancy or breast feeding or patients of child-bearing potential, including men with partners of child-bearing potential, who are unwilling

tudy Number: YF	C1-HEX-B1 V 2.2, Feb 6 th 202
udy Number: YF	after the medication. (Note: Child-bearing potential is defined as women who are ovulating, pre-menopausal or not surgically sterilized. All women of child-bearing potential must document a negative pregnancy test before study inclusion and use adequate contraception during the study). 6. Participation in other clinical studies with investigational drugs/investigational device either concurrently or within the last 30 days prior to the first study cystoscopy. 7. Patient who is the investigator or any sub investigator, research assistant, pharmacist, study coordinator, other staff or relative thereof directly involved in the conduct of the protocol.
	8. Patients that the investigator believed were unlikely to comply with the protocol.
	9. Subjects with contraindications to white light cystoscopy.
Drug / Device	Drug name: Hexvix (hexaminolevulinate hydrochloride, for intravesical solution, for bladder instillation only) as the photosensitizer to use with blue light cystoscopy Active ingredient: Hexaminolevulinate hydrochloride Device: Cystoscopic equipment with necessary filters to allow both standard white light cystoscopy and blue light (wavelength 380–450 nm) fluorescence cystoscopy
Comparative Drug	Not applicable
	Primary Efficacy Endpoint:
	• The proportion of patients with histology-confirmed tumors (Ta, T1, or CIS) who have at least one such tumor found by Hexvix but not by white light cystoscopy.
E.C. acces	Secondary Efficacy Endpoint:
Efficacy Endpoint	• The proportion of patients with one or more CIS lesions detected only by Hexvix blue light cystoscopy not by white light cystoscopy.

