1.2.2 Clinical Study

Belowing are brief presentation of Hexvix clinical studies, more information is available in the investigator brochure [12].

Blue light cystoscopy with Hexvix offers considerable benefits over white light cystoscopy in the detection of NMIBC. This has been supported by a number of clinical phase III trials [13,14,15], which have demonstrated that 16-29% of patients had one or more Ta or T1 tumor that were detected by blue light cystoscopy with Hexvix and not by white light cystoscopy. A pivotal phase III study showed that in 16% of the patients with Ta or T1 tumors at least one additional tumor was detected with blue light cystoscopy with Hexvix that was missed with white light cystoscopy (p=0.001) [15]. This phase III study also demonstrated that improved detection of Ta/T1 bladder tumors enables a more complete resection, resulting in a significant reduction of recurrence rates within 9 months. During the surveillance period, for ITT (the Intention-To Treat) analysis 128/271 patients (47%) in the Hexvix group and 157/280 patients (56%) in the white light group had tumor recurrence (p=0.026). The PP (Per Protocol) results were similar to those for the ITT group. The relative reduction in cancer recurrence at 9 months was 16% for the ITT analysis and 21% for the PP analysis. There was a trend that more patients in the group treated with white light only experienced recurrence of higher stage tumors (T1 or CIS) compared to patients treated with blue light cystoscopy with Hexvix.

Results from three phase III studies demonstrated that blue light cystoscopy with Hexvix improves the detection of CIS lesions significantly, which has consequences for patient management and may improve prognosis [11, 16, 17]. One study included 211 patients with suspicion or known bladder cancer. CIS lesions were found in 39% of evaluable patients and in 22% of these patients CIS lesions were detected only with blue light cystoscopy with Hexvix. Data from the other study showed that 30% of the patients had CIS and among these 16% were detected only by blue light cystoscopy with Hexvix.

Study Number: YHCT-HEX-B1

In the last study [17], among 26 patients with CIS, 34.6% had CIS detected only with blue light cystoscopy with Hexvix.

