7.1 Primary Efficacy Endpoint

The primary efficacy endpoint of this study as below:

• The proportion of patients with histology-confirmed tumors (Ta, T1, or CIS) who have at least one such tumor found by Hexvix but not by white light cystoscopy.

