7.2 Secondary Efficacy Endpoint

The secondary efficacy endpoint of this study as below:

- The proportion of patients with one or more CIS lesions detected with Hexvix blue light cystoscopy not by white light cystoscopy.
- The lesion detection rate of Hexvix blue light cystoscopy, compared to white light cystoscopy per lesion type (PUNLMP, CIS, Ta, T1, T2-T4).
- The proportion of false positive lesions detected with Hexvix blue light cystoscopy and white light cystoscopy.

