10.4.2.2 Secondary Efficacy Endpoints

Secondary efficacy endpoints analysis will be based on FAS and PPS.

Secondary efficacy endpoints will be analyzed descriptively, including event rate and 95% confidence intervals based on the FAS and PPS. Exact 95% confidence interval will be calculated similarly to that of the primary efficacy endpoint. But no formal statistical inference will be made to the secondary efficacy endpoints.

If the establishment of confidence intervals is based on biopsy/TURBT data, Bladder biopsy/TURBT data should be assumed to be independent of each other.

Efficacy data will be tabulated in detail.

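### Does the CIS secondary endpoint need a denominator written into the protocol?

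*Combined protocol and SAP*

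**What the plan says.** Section 7.1 builds the denominator into the primary endpoint: "The proportion of patients with histology-confirmed tumors (Ta, T1, or CIS) who have at least one such tumor found by Hexvix", where white light missed that tumour. Section 10.3.2.2 gives it a matching set, the mFAS, limited to blue-light subjects with confirmed Ta, T1 or CIS.

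The CIS endpoint has no such clause. Section 7.2 has "The proportion of patients with one or more CIS lesions detected with Hexvix blue light cystoscopy not by white light cystoscopy"; the synopsis has "The proportion of patients with one or more CIS lesions detected only by Hexvix blue light cystoscopy not by white light cystoscopy". The two differ only in the word *only*.

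For the analysis set, section 10.3.2.1 says "All secondary efficacy analysis will be based on full analysis set (FAS"), and section 10.4.2.2 says "Secondary efficacy endpoints analysis will be based on FAS and PPS". The FAS takes in non-training subjects who had the instillation and the blue-light examination. The PPS is a subset of it. Neither requires cancer or CIS.

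Section 10.4.2.2 adds "Exact 95% confidence interval will be calculated similarly to that of the primary efficacy endpoint". It also rules out formal inference on secondary endpoints and promises detailed tabulation of efficacy data. Section 10.1 leaves detailed methods to a statistical analysis plan finalised before the first database lock.

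**The concern.** The contrast with the primary endpoint is what catches the eye. The authors wrote a denominator there and defined a set to go with it; for CIS they did neither. A programmer working only from the set assignment could divide by the whole FAS.

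That rate would be CIS prevalence among enrolled subjects multiplied by the blue-light-only share among patients with CIS, so it would mix case mix with imaging performance. It would not by itself answer the objective in section 2.2 of comparing how the two methods find patients with CIS. Nor could it be set beside the figures in section 1.2.2, which are shares of patients with CIS: for one study, "CIS lesions were found in 39% of evaluable patients and in 22% of these patients CIS lesions were detected only with blue light cystoscopy", and for the other two, 16% and 34.6%. The per-lesion CIS detection rate, a separate endpoint, does not supply the missing patient-level denominator.

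At stake would be a reported percentage that readers could misread by an order of magnitude.

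**Working it through.** **1. The plan's own figures.** Section 10.2 assumes that 35% of subjects have bladder cancer, with "bladder cancer with Ta, T1 and CIS stage accounting for 75"% of it.

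- Ta/T1/CIS share of subjects: 0.35 × 0.75 = 0.2625, so 73.75% have none.
- Subjects needed: 94 / 0.2625 = 358.1, rounded up to the stated 359. With 5% drop-out, 359 / 0.95 = 377.9, stated as about 380. Both figures reproduce.
- Expected FAS, if the 94 are counted among blue-light subjects: about 358. Expected cancers of any stage: 0.35 × 358 = 125.3.

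**2. How the two readings relate.** Let π be the CIS prevalence in the FAS and s the blue-light-only share among patients with CIS. The FAS reading gives π × s and the CIS reading gives s, so they differ by a factor of 1/π. The factor does not depend on how many subjects are randomised out of blue light.

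**3. Size of the factor.** The plan states no CIS share for this trial. Assumed shares are 10% (section 1.1, of non-muscle-invasive disease) and 30% and 39% (section 1.2.2, earlier studies).

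| Assumed CIS share | Expected CIS patients | 1/π |
|---|---|---|
| 10% of Ta/T1/CIS | 94 × 0.10 = 9.4 | 1/(0.2625 × 0.10) = 38.1 |
| 30% of Ta/T1/CIS | 94 × 0.30 = 28.2 | 1/(0.2625 × 0.30) = 12.7 |
| 39% of Ta/T1/CIS | 94 × 0.39 = 36.7 | 1/(0.2625 × 0.39) = 9.8 |
| 30% of all cancers | 125.3 × 0.30 = 37.6 | 1/(0.35 × 0.30) = 9.5 |
| 39% of all cancers | 125.3 × 0.39 = 48.9 | 1/(0.35 × 0.39) = 7.3 |

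Applying 30–39% directly to all subjects gives only 3.3- to 2.6-fold, but it exceeds the plan's own 26.25%. The 10% puts each tumour in one category and may miss CIS that accompanies Ta or T1, so the 38-fold end is the least certain.

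**4. What each reading would report, with s near 22%** (Clopper-Pearson 95% intervals).

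| Blue-light-only CIS patients | Among CIS patients | Among 358 FAS subjects |
|---|---|---|
| 2 | 2/9 = 22.2% (2.8 to 60.0) | 0.6% (0.1 to 2.0) |
| 6 | 6/28 = 21.4% (8.3 to 41.0) | 1.7% (0.6 to 3.6) |
| 11 | 11/49 = 22.4% (11.8 to 36.6) | 3.1% (1.5 to 5.4) |

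**5. Does the FAS figure mainly follow prevalence?** Across the whole table, prevalence moves it 48.9 / 9.4 = 5.2-fold. With the 30–39% inputs alone it moves 48.9 / 28.2 = 1.7-fold, while s, from 16% to 34.6%, moves it 34.6 / 16 = 2.2-fold. The answer depends on the 10% input, so this claim is not secure.

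**6. Which reading the text supports.**

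- *Wording.* The phrase about patients with one or more CIS lesions can itself be the base of the proportion. Section 2.2 (detection of patients with CIS) and section 1.2.2 (shares of CIS patients) fit that.
- *Role of the FAS.* Section 7.2 lists three endpoints, all assigned to the FAS. Two of them, the detection rate per lesion type and the false-positive proportion, are counted in lesions, so FAS subjects cannot be their divisor. Section 10.4.2.2 even says what to assume when an interval rests on biopsy or resection data. The FAS there says whose data are used.
- *The interval sentence.* It carries over the exact method from the primary endpoint; it does not fix n.
- *The two wordings.* Both exclude detection by white light, so the missing *only* in section 7.2 is a clerical difference.

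**The case for a change.** The best case for a change is that a denominator is part of an endpoint's definition and should not be left to later documents. The gap is real: neither statement of the endpoint has it, no CIS-positive set is defined, and the only sets assigned, FAS and PPS, carry no CIS condition. Two readings an order of magnitude apart are possible. One sentence would settle the matter before results are known, at no cost in data.

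The missing denominator stands, as does the point that an all-FAS percentage would be a poor summary of CIS detection. What does not stand is that the plan has chosen that percentage. It never calls the FAS the divisor, and its own per-lesion endpoints show that it is not used that way. It also cannot be said that the figure will be undefined at database lock: section 10.1 places the detail in the analysis plan, and the text available here includes only the protocol's statistical section.

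Comparability with section 1.2.2 is a weak argument for new wording too. The plan does not set it as an aim, and the 16% can be read as patients whose CIS was found only under blue light. That is narrower than patients with at least one blue-light-only CIS lesion.

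**Conclusion.** No change to the plan is called for. What remains is an unwritten detail of a descriptive endpoint. An analyst who knows the objective would take FAS and PPS subjects with centrally confirmed CIS as the base, and the detailed tabulation required by section 10.4.2.2 should let either proportion be recovered. No hypothesis test depends on it, and the primary endpoint, its error rate and power, and the 94 patients are unaffected.

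If an all-FAS rate were printed alone, it would be about 7 to 38 times below the CIS-patient share. That range rests on CIS shares borrowed from the background sections, on section 10.2's 35% and 75%, and on the 94 all being blue-light subjects. It measures the gap between two readings, not an error in the plan. The conclusion would be weaker if the final analysis plan named all FAS subjects as the sole denominator; nothing in the text reviewed does so.
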